#### According to:

$$K = n_2 / n_1$$

$$n_1 = ((\sigma n_1)^2 + ((\sigma n_2)^2) / k) / (Z_{1-\alpha/2} + Z_{1-\beta})^2 / \delta^2$$

$$n_1 = x ; n_2 = K n_1$$

$\delta = |\mu_2 - \mu_1|$  = absolute difference between two means

$\sigma_1, \sigma_2$  = variance of mean 1 and 2

$n_1$  = sample size for group 1

$n_2$  = sample size for group 2

## Light-intensity Physical Activity and Arterial Stiffness in Type 2 Diabetes (LiPAT)

---

$\alpha$  = probability of type I error

$\beta$  = probability of type II error

$z$  = critical Z value for a given  $\alpha$  or  $\beta$

$k$  = ratio of sample size for group 2 to group 1

Rosner B. *Fundamentals of Biostatistics*. 7th ed. Boston, MA: Brooks/Cole; 2011

## **5. TREATMENT OF SUBJECTS**

### **5.1 Investigational product/treatment**

#### Intervention group

The goal of the LiPA intervention program is to increase LiPA by reducing sedentary time by making use of a feedback activity monitor that is described in more detail below. The aim is to reduce sedentary time roughly by 10% as compared to baseline. Given that participants are sedentary for on average 9.3 hours (560 minutes) per day, participants are encouraged to decrease their sitting time by replacing approximately one hour per day of sitting time with LiPA activities. Sedentary behaviour, standing, and stepping time will be objectively measured making use of the activPAL® activity monitor that will be worn for 7 days continuously at baseline, month 3, month 6, and month 12. This device is blinded to the participant. The activPal® is a commercially available research tool ([www.paltech.plus.com](http://www.paltech.plus.com)). Data from the activPAL provide detailed and accurate information on the participants' sedentary, standing, and stepping time for each day.

Participants in the intervention group will be invited for a workshop, as a group session with approximately 20 participants. During this first workshop, extensive attention will be paid to what LiPA itself is, what the potential health benefits of LiPA are and how it can be incorporated into daily life and thus increased. Generic strategies to increase LiPA over the whole day will be discussed with participants. In month 2 and 3 of the trial, two additional group sessions will be organized during which progress will be discussed and if necessary further advise on how to increase LiPA. In the last month of the trial a final group session is planned which is followed by an unsupervised follow-up of 6 months. During the workshops topics related to a healthy lifestyle are being introduced. This information is based upon general healthy lifestyle guidelines, exercise guidelines and diabetes guidelines (please see below) In addition this will be an opportunity for participants to share their experiences.

Participants in the intervention group will receive a feedback physical activity monitor (Fitbit inspire; commercially available consumer product (<https://www.fitbit.com/inspire>)). Participants will receive extensive instructions on its use, the internet interface and how it will provide feedback during the first group workshop. The Fitbit inspire is worn on the wrist like a wristwatch. It has a watch interface and it tracks movement tri-axially. The data is synchronized with the mobile phone app, with a protected cloud-based platform that collects and analyses data from the device. The app is designed to help the participant to self-monitor their physical activity levels and includes information on total activity, number of steps, kcals burned, and sleep parameters. Based on the collected data the investigators will be able to provide personalised recommendations to the participants with the use of

proprietary algorithms on activity levels and activity goals can be set. After the first week of data collection, information about participants' average activity is available which will be used to set an activity goal. This goal will be adjusted accordingly during the trial. For example if a participant has on average 4 hours of activity a day, a goal of 4,5 hour of activity a day could be set as an activity goal.

Furthermore, participants will be alerted automatically during the day (from 0800 to 2100 hrs) when he/she has been inactive for prolonged periods of time (based on an activity goal of 250 steps per hour). This should remind the participant to engage in LiPA.

Participants will be instructed to wear the activity monitor continuously, also during the night, to be able to monitor sleeping behaviour. Participants are advised only to take the device off when the battery has to be recharged. Data will be automatically transferred by Bluetooth to the mobile application and the protected cloud-based platform and internet interface so that the participant can monitor progress and, if so required additional e-feedback can be dispersed. If LiPA goals are met, participants will be automatically rewarded by means of positive (e-)reinforcement (e.g., by encouragement messages in the app ("Well done! You have met your LiPA goal!") and encouragement symbols (e.g., a smiley). There will be no negative messages dispersed to the participant if LiPA goals are not met. During the intervention, small (digital) prizes for encouragement (e.g. fruit basket or a digital "thumbs up") will be raffled among participants who reach their activity goals.

During the first month of the intervention, participants will get acquainted with the use of the Fitbit inspire and bi-weekly phone calls with participants are planned to monitor use of the feedback activity monitor and set LPA goals based on their habitual activity. After this run-in period, monthly phone calls with participants are planned during the second and third month to provide feedback on the Fitbit inspire use and to help participants to reach their LiPA goals with the use of the watch and web-based interface. As from month 4 onwards, no structural phone calls with participants are planned anymore and feedback rests entirely upon the digital platform as by choice of the participant. During the complete period of the intervention a manned help-desk is available for any questions by the LiPAT participants.

### Control group

Participants in the control group are, like the intervention group, invited for 4 workshops. These workshops are similar to the workshops of the intervention group, yet without the Fitbit inspire device. During the workshops topics related to a healthy lifestyle are being introduced. This information is based upon general healthy lifestyle guidelines, exercise guidelines and diabetes guidelines. Participants in the control group will not receive the e-feedback monitoring device. During the complete period of the study a manned help-desk is available for any questions by the participants about LiPA.

For safety reasons, for both the intervention and control group, a medical doctor (internist) is available (24/7) to discuss / advise on any alterations in the use of glucose lowering medication for both participant and general practitioners (or diabetes nurse practitioners). It can be expected that the most enthusiastic participants will experience alterations in their glucose levels which may require adjustment of their medication. Daily clinical care however remains the responsibility of the participant's own diabetes care provider either being the general practitioner or the diabetes nurse practitioner.

To note: the activPal ® ([www.Paltech.plus.com](http://www.Paltech.plus.com)) and Fitbit inspire (<https://www.fitbit.com/inspire>) are both commercially available research and consumer products and are incorporated into the trial as measurement tools but are themselves not part of the research aims of the current project. Both the ActivPal ® and the Fitbit inspire will be purchased by the investigational team from the respective companies.

### Overview of workshop contents:

#### Intervention group

Workshop 1 – month 1 (duration 2 hours)

Topics to be covered:

- the health risks of sedentary behaviour
- what is LiPA and what are the health benefits
- what are generic strategies to increase LiPA by reducing sedentary time
- introduction of the Fitbit inspire and the mobile application
- individual goal setting

Workshop 2 – month 2 (duration 1 hour)

- physical activity and a healthy lifestyle in type 2 diabetes; therapeutic benefits
- reflection of participants on their LiPA levels
- experience with the Fitbit inspire and the what is LiPA and how can it be increased
- activity levels and change in the workshop group (comparing participants' progress (anonymized))
- individual goal setting

Workshop 3 – month 3 (duration 1 hour)

- activity levels and change in the workshop group (comparing participants' progress (anonymized))
- group discussion on progress and discuss strategies to increase LiPA

## Light-intensity Physical Activity and Arterial Stiffness in Type 2 Diabetes (LiPAT)

---

- preparing for second part of the intervention without progress phone calls
- individual goal setting

### Workshop 4 – month 6 (duration 1 hour)

- looking back at the study
- activity levels and change in the workshop group (comparing participants' progress (anonymized))
- sharing LiPA progress
- Long-term maintenance of LiPA

### Control group

#### Workshop 1 – month 1 (duration 1 hour)

##### Topics to be covered:

- the health risks of sedentary behaviour
- what is LiPA and how can it be increased
- what are generic strategies to increase LiPA by reducing sedentary time
- how to goal set LiPA in general

#### Workshop 2 – month 2 (duration 1 hour)

- physical activity and a healthy lifestyle in type 2 diabetes; therapeutic benefits
- reflection of participants on their LiPA levels
- group anonymized group feedback without comparison

#### Workshop 3 – month 3 (duration 1 hour)

- group anonymized feedback without comparison
- group discussion on strategies to increase LiPA
- preparing for second part of the intervention without meetings or feedback at group level

#### Workshop 4 – month 6 (duration 1 hour)

- looking back at the study
- group anonymized feedback without comparison
- long-term maintenance of LiPA healthy lifestyle

## 6. METHODS

### 6.1 Study parameters/endpoints

#### 6.1.1 Main study parameter/endpoint

##### **Arterial Stiffness:**

The primary outcome variables in the LiPA-Trial will be pulse wave velocity (PWV; i.e., aortic [carotid to femoral] PWV) and carotid distensibility which will be determined with the use of applanation tonometry and arterial ultrasound, respectively. More details are described in section 8.2. The outcome variables will be determined at t = 0 (month 0; baseline visit), t = 3 (month 3, first investigational visit), t = 6 (month 6; second investigational visit) and t = 12 (month 12; third investigational visit (end of the trial)).

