#### **Main study parameters/endpoints:**

The primary outcome is pulse-wave velocity and carotid distensibility which will be determined with the use of applanation tonometry and arterial ultrasound. The effect of the intervention on the primary outcome PWV at month 6 will be analysed.

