## 2. OBJECTIVES

### Primary Hypothesis:

A LiPA intervention program based upon increasing LiPA by replacing sedentary time (approx. 1 hour) is effective in a) lowering arterial stiffness as estimated by aortic PWV and carotid distensibility and b) enhance microvascular function as estimated by retinal photos and skin heat-induced hyperemia in individuals with T2D.

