### 4.4 Sample size calculation

For the primary objectives of the study:

to be able to detect a 10% difference in PWV after the intervention between the intervention group and the control group set against a probability of a type 1 error at 0.05 (i.e.,  $\alpha$ ) and the ability to detect a true difference between the intervention group and the control group set at 80% (i.e.,  $\beta$ ) both groups should consist of a minimum of 73 participants each. These estimates are conservative taking into account only PWV values at entry and exit of the trial. The 10% difference is speculative and based upon a mean PWV estimates from The Maastricht Study data as there is currently no data available on LiPA and arterial stiffness. For reasons of efficiency in addition to potential drop (roughly estimated at 10%) out we will include in each group 80 participants

to be able to detect a 10% difference in carotid distensibility after the intervention between the intervention group and the control group set against a probability of a type 1 error at 0.05 (i.e.,  $\alpha$ ) and the ability to detect a true difference between the intervention group and the control group set at 80% (i.e.,  $\beta$ ) both groups should consist of a minimum of 73 participants each. These estimates are conservative taking into account only carotid distensibility values at entry ( $t = 0$ ) and exit of the investigational period of the trial ( $t = 6$ ). The 10% difference is speculative and based upon mean estimate from The Maastricht Study data as there is currently no data available on LiPA and arterial stiffness. For reasons of efficiency in addition to potential drop (roughly estimated at 10%) out we will include in each group 80 participants.

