### **8.1 Primary study parameter(s)**

The effect of the intervention on the primary outcome PWV at month 6 will be analysed using intention-to-treat (ITT) approach according to randomization assignment. The ITT analyses will be used as primary method for our statistical analyses and any outcomes in our reports will be primarily based upon these ITT analyses. In addition, a per protocol analysis will be performed for those who attended the workshops. These analyses will be used to gain some insights into any potential non-response / drop out. These per protocol analyses will not be the primary source for reporting outcomes. General linear models will be used to analyse the effect of the intervention on PWV at month 6. Due to the COVID-19 crisis some month 6 measurement will take place at a later moment, depending on the duration of this delay we will have to adjust for this in our statistical analyses. In addition, repeated measures will be taken into account, baseline, month 3, and month 6 using mixed models in SPSS. The 3-month visits might be missing for some participants due to COVID-19 crisis, we assume that the 6-month measurements for these participants can take place as planned. In these models, subject is entered as a random effect and intervention (categorical variable with 2 levels: 1: intervention; 2: control group) as a fixed effect. The baseline value of PWV and sex will be used as covariates in analyses.

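### The protocol contradicts itself on the primary outcome: PWV and carotid distensibility are both primary in some sections, month-6 PWV is the only one named and modelled in others

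*Protocol*

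**What the plan says.** Four places in the protocol treat aortic PWV and carotid distensibility as both primary.

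- Section 6.1.1: "The primary outcome variables in the LiPA-Trial will be pulse wave velocity (PWV; i.e., aortic [carotid to femoral] PWV) and carotid distensibility".
- Summary, endpoint paragraph, first sentence: "The primary outcome is pulse-wave velocity and carotid distensibility".
- Section 2, primary hypothesis: "a) lowering arterial stiffness as estimated by aortic PWV and carotid distensibility".
- Section 4.4, opened by the plural "For the primary objectives of the study". It gives one calculation for PWV and a second one "to be able to detect a 10% difference in carotid distensibility after the intervention between the intervention group and the control group". Each uses a type I error of 0.05 and 80% power, and each arrives at 73 per group.

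Two places name PWV only.

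- Summary, endpoint paragraph, the very next sentence: "The effect of the intervention on the primary outcome PWV at month 6 will be analysed".
- Section 8.1: "The effect of the intervention on the primary outcome PWV at month 6 will be analysed using intention-to-treat (ITT) approach". The month-6 model that follows is written for PWV, with baseline PWV and sex as covariates.

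Section 8 sets a single significance level of 0.05. Carotid distensibility is named nowhere in section 8, neither under the primary parameters (8.1) nor under the secondary ones (8.2). It is also absent from the secondary endpoints in section 6.1.2.

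**The concern.** The set of primary outcomes decides what counts as a positive trial. If PWV misses and distensibility is significant, section 8.1 reads as a failed trial, while section 6.1.1 offers a primary outcome that succeeded. If PWV is significant and distensibility misses, section 8.1 reads as success, while the hypothesis and section 4.4 can be read as only half met. Each report would have protocol text behind it, and the choice could be made after the data are seen.

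A statistical analysis plan may properly add a testing rule to a defined set of endpoints. Here the protocol disagrees with itself about the set, so the protocol is where it has to be settled.

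**Working it through.** **Inputs from the protocol.** Section 4.4: two-sided alpha 0.05 (its formula uses Z for 1-α/2), power 80%, equal groups, a 10% difference and 73 per group, the same for each outcome. No mean or SD is given for either outcome.

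**The plan's own figure.** Without an SD, 73 cannot be reproduced. It can only be solved backwards. The standardized difference detectable with 73 per group is (1.960 + 0.842) × √(2/73) = 0.464. A 10% difference then corresponds to an SD of about 10/0.464 = 21.6% of the mean. I take section 4.4 at its word and give each outcome exactly 80% power at 73 per group, that is, a noncentrality of 1.960 + 0.842 = 2.802.

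**Model.** The two test statistics are bivariate normal with correlation r. The protocol gives no r, so values from 0 to 0.9 are assumed.

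1. *PWV alone.* Error 0.05, power 0.80, as planned.
2. *Both required.* Error is at most 0.05. Joint power is P(Z₁ > 1.96 and Z₂ > 1.96) with both means at 2.802. At r = 0 this is 0.80 × 0.80 = 0.64.
3. *Either sufficient, each at 0.05.* Error is 1 − P(|Z₁| < 1.96 and |Z₂| < 1.96) with both means at 0. At r = 0 this is 1 − 0.95² = 0.0975.

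| Assumed r | Joint power, both required | Error, either sufficient |
|---|---|---|
| 0 | 0.640 | 0.0975 |
| 0.3 | 0.666 | 0.0951 |
| 0.5 | 0.687 | 0.0907 |
| 0.7 | 0.713 | 0.0835 |
| 0.9 | 0.750 | 0.0704 |

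The same 73 per group therefore means 80% power under one definition and 64% to 75% under the other.

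**The case against.** **Section 8.1 may be incomplete rather than contradictory.** It never says that PWV is the sole primary, its heading allows for more than one parameter, and section 6.1.2 does not list distensibility as secondary. The general provisions (intention to treat, imputation, month-12 analysis) could cover it. On this reading an analysis plan could extend the PWV model to distensibility and add a rule. That much is fair, and it would go too far to say that no analysis plan could bridge the gap. But section 8.1 and the Summary both use the singular for PWV, and the Summary holds the two definitions in adjacent sentences. No passage says that distensibility is a second primary in the analysis.

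**A reader might infer that the protocol allows success on either outcome, with error up to 9.75%.** The text does not go that far. The Summary, the hypothesis and section 6.1.1 join the outcomes with *and*, never *or*. The two readings closest to the text both hold 5%. The 9.75% to 7.0% belongs to a rule left open by silence.

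**A reader might infer that baseline adjustment restores joint power to 80%.** The protocol does not allow that to be worked out, because it does not say what SD lies behind 73. Section 4.4 says only "These estimates are conservative taking into account only PWV values at entry and exit of the trial", which fits an SD of final values or of change scores. At an assumed baseline to month-6 correlation of 0.7 and r from 0 to 0.9, a final-value SD makes the noncentrality 2.802/√(1 − 0.49) = 3.92 and joint power 95% to 97%. A change-score SD makes it 2.802 × √(2/1.7) = 3.04 and joint power 74% to 82%. Any adjustment would also raise the power for PWV alone, so an adjusted joint power must not be set against an unadjusted 80%.

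**The primary hypothesis is loose drafting.** Its part b) adds microvascular function, which sections 2 and 6.1.2 treat as secondary. This weakens the hypothesis as evidence for exactly two primaries. Sections 6.1.1 and 4.4 carry the point without it.

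**Conclusion.** The contradiction stands, rests on the protocol's own words and needs correcting before outcome data are analysed. PWV alone has 5% error and 80% planned power. Both required has error of at most 5% and unadjusted joint power of 64% to 75%, against the 80% stated per outcome. An either-outcome rule is unstated but not ruled out.

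The power figures rest on section 4.4's claim of 80% per outcome at 73 per group, which cannot be checked without an SD, and on assumed between-outcome correlations of 0 to 0.9. The contradiction itself depends on none of these numbers; they show only that the choice matters. It is not established that the trial is too small or that its error rate is inflated. That depends on which definition the sponsor adopts.

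**What to change.** Amend the protocol before outcome data are analysed, so that the Summary and sections 2, 4.4, 6.1.1 and 8.1 carry one definition.

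**Low-cost choice.** Name aortic PWV at month 6 the single primary outcome, as section 8.1 already has it. Test carotid distensibility at month 6 second, at 0.05 and only if PWV is significant, with the same model adjusted for its own baseline value and sex. Relabel the distensibility paragraph in section 4.4 to match. This holds the error at 5% across the two tests and costs PWV no power.

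**Alternative.** Keep two primaries, state in sections 6.1.1 and 8.1 that both are required, name distensibility in the 8.1 model, and restate the power in section 4.4 as joint power with its assumptions (SD, type of outcome, correlation).

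**Cost.** One amendment notified to the ethics committee under section 10.3, since the COVID-19 text in sections 3 and 8.1 shows that the trial was under way. The low-cost choice is wording only, with no extra patients or visits. Its downside is that distensibility cannot be claimed if PWV fails; the chance of claiming it equals the joint power, 64% to 75% unadjusted. The alternative may or may not need more patients, depending on the SD and correlations that the sponsor can document.

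Two editorial points can go into the same amendment but are separate. Part b) of the primary hypothesis should be reconciled with the secondary objectives. The cross-reference from section 6.1.1 to 8.2 should most naturally point to the measurement detail in section 6.3.

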#### 6.1.2 Secondary study parameters/endpoints (if applicable)

##### **Microvascular function:**

Microvascular function will be evaluated in both the retina and the skin. Which will be determined with the use of fundoscopy and Skin laser Doppler flowmetry. The outcome variables will be determined at t = 0 (month 0; baseline visit), t = 3 (month 3, first investigational visit), t = 6 (month 6; second investigational visit) and t = 12 (month 12; third investigational visit (end of the trial)).

##### **Blood pressure:**

Any changes in blood pressure and blood pressure lowering medication determined at t = 0 (month 0; baseline visit), t = 3 (month 3, first investigational visit), t = 6 (month 6; second investigational visit) and t = 12 (month 12; third investigational visit (end of the trial)) determined with the use of the705-IT (Omron Healthcare (oscillometric blood pressure device)).

